Inclusion/Exclusion Criteria:	Patients will be included in the study if they meet the following inclusion criteria: 1. At least one prescription of Mysimba/Contrave in his/her medical records any time during the study period; 2. At least 365 days of computerized records prior to first prescription/dispensing of Mysimba/Contrave (index date); and 3. Patient is active (i.e., alive and registered/accruing data) at index date.			
	All patients meeting inclusion criteria will be included in the study; no exclusion criteria will be applied.			
Safety Assessments:	The incidence rate of adverse events of special interest (AESI) per person-years of exposure after initiation of Mysimba/Contrave will be assessed. Additionally, overall and for each type of AESI, the crude incidence of new AESIs will be reported as the incidence proportion, which will be reported over the empirical follow-up time and with 95% CI.			
Data Analysis:	For demographic and baseline variables, descriptive statistics will be used to describe categorical and continuous variables. Descriptive analyses will be performed for all users of Mysimba/Contrave, and by use categories: (1) use inconsistent with the approved indication, and (2) use incompatible with the stated contraindications. The incidence rate (and 95% CI) of new onset comorbidities and concomitant medication after initiation of Mysimba/Contrave will be assessed. Incidence rates will be determined both for the person-years of time exposed to Mysimba/Contrave (i.e., while patient taking medication) after the index date as well as for all person time through 548 days (18 months) after the index Mysimba/Contrave prescription.			

The incidence rate (and 95% CI) of pregnancy and recorded breastfeeding after the Mysimba/Contrave index date will be assessed among females initiating Mysimba/Contrave.
The mean, standard deviation, median, mode, and interquartile range of Mysimba/Contrave medication duration will be assessed overall and by use categories. Among patients with available information, the proportion of patients with titration and dosing changes in alignment with the SmPC will be calculated.

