- 6. Serotonin syndrome
- 7. Major adverse cardiovascular events (i.e., cardiovascular-related death, non-fatal myocardial infarction, or non-fatal stroke)

Deaths will also be described by treatment group, for those with vital status available.

- 7. Treatment discontinuation (assessed using ATC [outpatient, Nordic data] or NDC [US data])
- 8. Reason(s) for treatment discontinuation (obtained via ICD-10 codes in the 90 days prior to discontinuation)

All variables will be identified from the data sources via a pre-specified list of definitions (i.e., code lists; see Appendix 2). Occurrence of AESI based on diagnostic codes will be summarized for all patients, and for a subgroup of patients who do not adhere to conditions of the EU SmPC for the Scandinavian countries (adapted to local SmPC as needed) or to the FDA SmPC for the US. Such criteria include: not meeting appropriate criteria for the indication [obese (BMI \geq 30 kg/m²), or being overweight (BMI \geq 27 kg/m² to < 30 kg/m²) and having at least one weight-related co-morbidity (e.g., type 2 diabetes, controlled hypertension, or dyslipidemia) based on diagnostic codes. If BMI is not available, diagnostic and procedure codes for obesity and weight loss will be applied, recognizing that it will likely produce a more obese population than would be identified by BMI. Subgroup analyses will also be conducted to assess continuous treatment in patients with either renal or hepatic impairment.

Initiation of specific medications that could result with the occurrence of an event corresponding to an AESI (e.g., newly initiating anti-epileptic/seizure medication, newly initiating medications indicated for mania or depression) will also be tabulated. For hepatotoxicity, liver function tests can be used (when available) in addition to diagnostic codes.

For reason(s) patients who discontinue treatment (i.e., do not refill their prescription), events (potential AESIs and contraindications) and clinical status (magnitude of weight loss or gain)

Proprietary and Confidential:

occurring within the 90-day window prior to discontinuation will be summarized. It should be noted that weight may not be available in the Scandinavian registries.

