To allow for multiple cycles of Mysimba/Contrave use and assessment of outcomes after initial exposure, the follow-up window for data collection after the index date will be up to 548 days (18 months), as an appropriate time-horizon for this specific purpose. All patient time during the follow-up window will be captured and censoring will occur at the earliest of death, disenrollment, 548 days of follow-up, or end of the study period (December 31, 2023).

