All citizens of these countries are represented in these national registries until death or emigration, providing virtually complete long-term follow-up. Identification of individuals by their unique personal identifier permits linkage to other national health databases (Laugersen et al., 2021). Thus, a large amount of specialized information from specific registries, such as hospitalization, prescription, heart disease, and death registries, can be linked for research (Schmidt 2015; Laugersen et al., 2021). The registries are highly complete and accurate due to the automation of their processes, as well as laws and other incentives motivating healthcare providers to collect and send the data electronically to their national databases (Gribsholt et al., 2019). The data from each country are expected to contain sufficient information to elucidate occurrence and determine levels of all variables, with the following exceptions which may be prone to misclassification due to limited coding in administrative and clinical data: obese or overweight with at least one comorbidity, neuropsychiatric conditions, history or current substance use or dependence, breastfeeding status, initial titration scheme and dose adjustments (expected to be unavailable since only one dose/pack type is available in the Nordic countries and no measure of titration scheme or adherence is included within the data), and reason(s) for medication discontinuation. Any country database with at least 750 patients with at least 365

days of data before the index Mysimba use and at least 548 days of availability in the data after the index date of Mysimba will be evaluated for whether there is sufficient required patient data to conduct this study. If there is sufficient data and uptake indicating that the database will reach more than 3,000 patients within the timespan of this drug utilisation and safety study, then it will be added to the data sources for evaluation. It should be noted that reimbursement varies in Scandinavia, with no reimbursement for Mysimba in Sweden and Denmark, and reimbursement in Norway and Finland restricted to morbidly obese patients who are at higher risk of cardiovascular and other events.

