9.7. Data Analysis

9.7.1. Timing of Feasibility, Interim, and Final Analyses

Prior to study start, feasibility was conducted annually.

One cohort per country will be extracted each time the database is opened. Per database, the following analyses will be conducted:

- 1. ongoing data review, for each of the participating Nordic countries
- 2. a first (interim) analysis when a database size reaches 750 patients with up to 548 days of activity in database after index date
- 3. a second (interim) analysis when an additional 2,250 patients (total 3,000 patients) with a Mysimba/Contrave index date are included in a database with up to 548 days of calendar time available in the database after the index date
- 4. a final analysis of the database will be conducted for the final report including all patients from the EU data sources meeting the inclusion criteria for the study as of 15 February 2025. If >3000 patients are available at the time of an interim analysis, the final report for

that database will be submitted one year after data is accessible. If final data is available 31 Dec 2024, the final report will be submitted by 31 Dec 2025.

All analyses will be performed separately in each country. All patients in the study will be included in the analysis, regardless of whether there is evidence of any contact with the health system (as registered by any data in the database) after inclusion into the study. One interim and one final analysis will be conducted per country. A final report will be generated when the last database in the study conducts the final analysis (when the last database has >3000 Mysimba patients, or 31 Dec 2025, whichever comes first). The final analysis from the four participating Nordic countries will be included in that report which will be accompanied by synthesis of findings, discussion, and interpretation across all Nordic databases.

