9.7.2. Descriptive Statistics

For demographic and baseline variables and duration of Mysimba/Contrave use (measured as both continuous treatment of the initial Mysimba/Contrave duration and the total treatment duration of Mysimba/Contrave), descriptive statistics will be used to describe continuous variables, (e.g., mean, standard deviation, median, quartiles 1 and 3, minimum, maximum, and two-sided 95% confidence intervals [CI]). Categorical variables will be described by the total and percentage of each response and the number of missing data (data that are unavailable in the database).

Patterns of Mysimba/Contrave use will be described by mean (standard deviation, SD) and median (quartile1, quartile 3) number of prescriptions per patient, number and duration of treatment episodes per patient as well as the average duration between prescription episodes. Analyses will be performed for all users of Mysimba/Contrave, including an assessment of whether the subjects have adhered to the prescribed treatment with Mysimba/Contrave according to the terms of the SmPC (adapted to the local country SmPC for the data source as needed, and adapted if BMI is not accessible). The number and proportion of patients who received treatment with Mysimba/Contrave will be provided according to the following subgroups (availability of variables to be summarized in SAP):

(a) Inconsistent with labelled indication:

- 1) Age < 18 years
- 2) Use other than management of weight
- 3) Management of weight in a patient who does not have obesity or is not overweight and has a weight-related comorbidity
- 4) A prescribed maintenance dose other than the Mysimba/Contrave 32mg/360mg
- 5) Continued use past 16 weeks without \geq 5% weight loss
 - (b) Incompatible with the stated contraindications set out in the SmPC:
- 1) A current diagnosis of uncontrolled hypertension, seizure disorder (or history of seizures), or end-stage renal failure
- 2) A history bipolar disorder, anorexia nervosa or bulimia
- 3) A current dependence on chronic opioids or opiate agonists (e.g., methadone)
- 4) A current state of acute opiate withdrawal
- 5) Any concomitant treatment containing bupropion, naltrexone, or a MAOI
- 6) Patients with a known central nervous system tumour
- 7) Patients undergoing acute alcohol or benzodiazepine withdrawal
- 8) Patients with severe hepatic impairment

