9.7.3. Incidence Rate of AESIs

The incidence rate of AESIs per person-years of exposure after initiation of Mysimba/Contrave will be assessed. Person-time of exposure will be calculated as the duration from the index date through the date of last Mysimba/Contrave prescription or dispensation (i.e., total treatment duration of Mysimba/Contrave), as applicable, plus 4 weeks. The number of cycles of Mysimba/Contrave during the exposure period will be summarized comparing all users, irrespective of their treatment duration status.

For each type of AESI, the crude incidence of new AESIs will be reported and the incidence proportion and 95% CI of will be estimated as the number of patients experiencing each type of event during Mysimba/Contrave exposure divided by the number of patients initiating treatment with Mysimba/Contrave. The proportion will be reported per 1,000 persons. The incidence density rate and 95% CI of AESI will be reported per 1,000 per person-years, using the sum of the person-years of the at-risk population as the denominator.

Further, clinical events of interest that might be associated with the occurrence of a potential AESI (e.g., newly initiating anti-epileptic/seizure medication, newly initiating medications indicated for mania or depression) will also be tabulated. For hepatotoxicity, liver function tests can be used (when available) in addition to diagnostic codes.

For reason(s) patients who discontinue treatment (i.e., do not refill their prescription), clinical events and health status occurring within the 90-day window prior to discontinuation will be summarized.

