9.7.4. Titration, Change in Dose, and Discontinuation

Among patients with available information, the proportion of patients with titration and dosing changes in alignment with the EU SmPC will be calculated. The local SmPC for the country of the data source may be used, if different than the EU SmPC.

Because reason discontinuation is rarely found in real world data, clinical events of interest and health status occurring within the 90-day window prior to discontinuation will be summarized for patients who discontinue treatment (i.e., do not refill their prescription). However, attribution to product is not possible.

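### Discontinuation is defined as not refilling, without the protocol's own episode-gap or censoring rules, and duration is summarised as if every patient's treatment had been observed to its end.

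*Protocol*

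**What the plan says.** **Discontinuation.** Section 9.3.2 describes the patients whose preceding 90 days are searched for reasons: "For reason(s) patients who discontinue treatment (i.e., do not refill their prescription), events". Section 9.7.3 has "For reason(s) patients who discontinue treatment (i.e., do not refill their prescription), clinical events and health status", and Section 9.7.4 says that such events "will be summarized for patients who discontinue treatment (i.e., do not refill their prescription". No gap length, observation requirement or treatment of restarts accompanies any of the three.

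**Episodes.** Section 9.3.1.1 works differently. An episode continues across a gap of up to half the preceding days' supply. After a longer gap it is closed, and later episodes are recorded separately. The worked example is a patient with episodes of 106 and 45 days.

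**Duration.** The Synopsis states: "The mean, standard deviation, median, mode, and interquartile range of Mysimba/Contrave medication duration will be assessed overall and by use categories". For duration as for baseline variables, Section 9.7.2 says that "descriptive statistics will be used to describe continuous variables, (e.g., mean, standard deviation, median, quartiles 1 and 3, minimum, maximum", with confidence intervals. Neither names a summary that allows for censoring.

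**Observation time.** Section 9.3.2 states that "censoring will occur at the earliest of death, disenrollment, 548 days of follow-up, or end of the study period (December 31, 2023". Section 9.1.1 sets no minimum follow-up, Section 9.2 takes whatever is available up to 548 days, and Section 9.7.1 triggers the first interim on patients "with up to 548 days of activity in database after index date". The phrase "at least 548 days of availability in the data after the index date" in Section 9.4.1 serves to qualify a database. Similar wording in 9.1 and 9.4 also concerns data sources. Section 9.7.1 puts all study patients in the analysis.

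**The concern.** Every patient has a last fill. If stopping means only that no refill followed, the rule cannot separate a patient who stopped from one whose observation ended first. The 90-day look-back would then mix events preceding a real stop with events preceding death or an administrative cut-off. For a patient who stops, perhaps after an adverse event of special interest, and restarts months later, the look-back would attach to the final fill and miss the earlier stop.

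For duration, treatment cut short by the end of observation is entered as if complete, which pulls the mean and median down. The pull depends on how many patients started late relative to the data cut, so it can differ between databases and between interim and final reports for reasons unrelated to patients.

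Duration of use, reasons for discontinuation, and adverse events of special interest that may have led to it are all stated secondary objectives.

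**Working it through.** **1. The protocol's own example.** The second episode in 9.3.1.1 is 225 − 180 = 45 days and the total is 106 + 45 = 151 days, as stated. This patient has one stop before the restart. Under the gap rule, the first episode has ended. Under the no-refill wording, the patient did refill after it, so that stop is not a discontinuation and its 90-day window is not examined. The two rules give different answers for the protocol's own illustrative patient.

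**2. Can patients have less than 548 days?** The study period ends on 31 December 2023 (9.3.2). Counting back 548 days gives 1 July 2022, so a patient indexed after that date cannot reach 548 days. The projected counts in 9.4.1.1 to 9.4.1.4 are stated as of 31 December 2023, the day on which follow-up ends. For the US, patients are counted to 31 December 2022 (9.4.2) and data receipt is anticipated on 15 February 2023 (Section 6). Counting back 548 days gives 16 August 2021. Death and disenrolment shorten follow-up further. Incomplete observation is therefore built in.

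**3. Illustrative size.** The protocol gives no persistence or accrual figures, so these inputs are assumptions: time on drug T exponential with median M months, λ = ln 2 / M; entry uniform over A months up to the data cut; observation C = min(18, U), with U uniform on (0, A). Then:

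- Share on drug when observation ends: P(T > C) = (1/A)·(1 − e^(−18λ))/λ + ((A − 18)/A)·e^(−18λ).
- Plain median m of min(T, C): e^(−λm)·(1 − m/A) = 0.5.
- 18-month restricted mean: R = (1 − e^(−18λ))/λ.
- Plain mean: R − (1/A)·[1 − e^(−18λ)(1 + 18λ)]/λ².

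For M = 6: λ = 0.1155, e^(−18λ) = 0.125, R = 7.57 months. With A = 36, P(T > C) = 7.57/36 + 0.5 × 0.125 = 0.210 + 0.0625 = 0.27.

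| True median (months) | Entry period (months) | Still on drug at end of observation | Plain median (months) | Plain mean ÷ restricted mean |
|---|---|---|---|---|
| 6 | 36 | 27% | 4.8 | 0.83 |
| 6 | 48 | 24% | 5.0 | 0.87 |
| 6 | 60 | 21% | 5.2 | 0.90 |
| 12 | 36 | 49% | 7.8 | 0.79 |
| 12 | 60 | 43% | 9.1 | 0.88 |

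**4. Separating the two effects.** If everyone had the full 18 months, the plain mean would equal R and the median would be unbiased at these values, so the duration bias would vanish. The labelling problem would not: at M = 6, 12.5% would still be on drug at the end of the window, and the no-refill wording would call them stopped. In days, 2^(−548/M) gives 1.5%, 12.1% and 35.3% for medians of 90, 180 and 365 days.

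**The case against.** The strongest reply is that the no-refill phrase is a short gloss and not a derivation. Appendix 3 lists discontinuation and its date as calculated in every source, with the variable list to be settled in the SAP, and 9.3.2 does state censoring. Nowhere does the protocol say that censored patients are to be called stoppers. This stands in part: the mislabelling follows from the literal text and is not a declared intention. But the gloss appears three times, it is the only definition attached to the reasons summary, and it differs from the rule in 9.3.1.1. An SAP that handled this correctly would have to depart from the protocol's wording.

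Four stronger readings are tempting, and the document does not support them.

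- A reader might infer that patients who restart are never counted as stopped. Their final fill is also unrefilled, so they are counted then. What is lost is the earlier stop, and only in the reasons summary. Duration handles restarts, because 9.3.1.1 closes the episode and records the next one.
- A reader might infer that a plain mean or median is wrong in itself. Total duration is defined within the 548-day window, and for fully observed patients the plain mean is a valid restricted mean. The list in 9.7.2 is also given as examples, although the Synopsis list is not.
- A reader might infer bias between compliant and non-compliant users. Nothing in the protocol shows that their follow-up would differ.
- A reader might take the percentages as estimates for this study. They rest on assumed persistence and accrual.

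The protocol also concedes that reasons for stopping are rarely recorded and that attribution to the product is not possible. This lowers what the reasons table can show, but does not justify filling it with patients who had not stopped.

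**Conclusion.** The point holds in this form. The no-refill wording in 9.3.2, 9.7.3 and 9.7.4 is tied neither to the episode gap in 9.3.1.1 nor to the stated censoring. Followed literally, it lets patients censored or dying on drug enter the 90-day reasons summary and omits a stop that is followed by a restart. The plain duration summaries are sound for patients observed for 548 days and biased low for the rest, whom the protocol admits. That bias varies with accrual timing across databases and between interim and final reports.

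Its size cannot be stated for this study. Under exponential persistence with a 6-month median and uniform entry over 36 to 60 months, the plain median is about 4.8 to 5.2 months, the plain mean is 10% to 17% below the 18-month restricted mean, and 21% to 27% of patients are still on drug when observation ends. The change should be made, since three secondary objectives depend on these definitions.

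**What to change.** - **One definition in 9.3.2, 9.7.3 and 9.7.4.** Discontinuation is the end of an episode under the 9.3.1.1 gap rule, in a patient alive and under observation through the whole permitted gap. Disenrolment, day 548 and data end are censoring, not discontinuation.
- **Reasons summary.** Take the 90-day window before the first discontinuation, and report restarts separately.
- **Initial-episode duration.** Add a censoring-adjusted summary. Either use the Kaplan-Meier median and 548-day restricted mean of time on treatment, with treatment ending at discontinuation or death, or use the cumulative incidence of discontinuation with death as a competing event.
- **Total days of use within 548 days.** Keep this for all patients, in line with 9.7.1, label it as observed days, and show it beside the distribution of follow-up. As a sensitivity analysis, repeat it in patients whose index date allows a full 548 calendar days before data end. Select on potential follow-up, so that deaths and leavers are not removed.

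The cost is protocol and SAP wording and slightly more analysis, using standard procedures on data already planned for extraction.

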9.3. Variables

9.3.1. Exposure

Exposure to Mysimba/Contrave will be identified through medication prescription or dispensing data (i.e., prescription or dispensing date, dosage [where available], and duration [where available]). The first Mysimba/Contrave prescription after 365 days with no prescription will be the index date, as depicted in Figure 1. All prescriptions of Mysimba/Contrave (or the two component products dispensed within 15 days) during the 548 days (18 months) following the index date will be captured. Patients will be assessed during the entire 548 days following the index date.

Figure 1. Index date, Exclusion and Covariate Assessment, and Follow-up Time for Study

Index Date (First prescription of Mysimba) Day 0

- a. Data are 'acceptable for research' for the patient and practice, coverage with computerized records throughout time period with no gaps
- b. Baseline conditions included: BMI, height, most recent weight, weight-related comorbidities (e.g., diabetes, dyslipidaemia), neuropsychiatric conditions (mania, bipolar disorder, major depressive disorder [MDD], anorexia nervosa, bulimia), hypertension, end-stage renal disease, seizure disorder, hepatic impairment (defined by Child-Pugh score category), central nervous system tumour, substance use/abuse including acute opiate withdrawal,;uncontrolled hypertension, seizures, bipolar disorder, MDD, anorexia nervosa, or bulimia; use of: naltrexone, bupropion, opioid or opiate agonist, or MAOI; pregnancy, or breastfeeding
- c. Earliest of: death, disenrollment, 548 days of follow-up, end of the study period

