9.4.1.3. Norwegian Health Registries

The Norwegian Prescription Database (NorPD) includes data on all prescription drugs dispensed in Norway since January 1, 2004 and is controlled by the Norwegian Institute of Public Health (NIPH). Pharmacies electronically register prescriptions to the NorPD via Statistics Norway on a monthly basis. The residents' national ID number and the prescribing provider's ID number are

replaced by a pseudonym to link drug use to individuals and other registries data while protecting patient identity. The NorPD will be linked with other Norwegian Patient Registries with information that includes demographic information of the patient (sex, year of birth, and municipality of residence), place and time of treatment, diagnoses, medical procedures, and reimbursement information of medical care.

Based on current and projected Mysimba prescription counts as estimates obtained during the last annual feasibility assessment and reimbursement in Norway restricted to the morbidly obese, we anticipate that this database may include >3,000 new users of Mysimba who will be eligible for inclusion in the study as of December 31, 2023 (to be confirmed when data access is granted). A final analysis of the database will be conducted for the final report including all patients meeting the inclusion criteria for the study as of 31 December 2024 (final report available 31 December 2025).

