9.4.2. United States Data Source

An EHR or claims-based integrated database across multiple healthcare systems in the United States, providing a representative mix of US Commercial Insurance and Medicare (major systems of health insurance in the US) has been selected. Arcadia Data Research was chosen as the US data for this study because of their approximately ten-year history of successfully curating data for health systems that are substantially involved in value-based care, which necessitates high-quality clinical data across the included patient populations. Data incorporated into the US dataset will include electronic medical records from multiple systems, laboratory test orders, and prescription data. Moreover, a sizeable proportion of the EHR population will also have their health insurance claims records linked in their final (adjudicated) form. The typical data extract will include (but is not limited to): patient demographics and characteristics (including height and weight or BMI if available), medical encounters, appointments, provider data, charges, assessments, immunizations, health maintenance and medical history, laboratory orders/results, vital signs (e.g., blood pressure, heart rate), patient insurance, prescriptions and active medications, problem lists, and patient allergy information. EHR data are sourced from large integrated delivery networks, academic medical centres, ambulatory care, primary care, core hospitals, and others. The data are coded in standard vocabularies used within the US, including ICD-10, NDC, CPT, LOINC, etc. Additional information, such as social determinants of health will be captured, if available. The data are expected to contain sufficient information to elucidate occurrence and determine levels of all variables, with the following exceptions which may be prone to misclassification due to limited coding in administrative and clinical data: neuropsychiatric conditions, history or current substance use or dependence, breastfeeding status, and reason(s) for medication discontinuation.

The integration of claims data for a subset of patients will be important for this study in order to capture pharmacy prescriptions dispensed and for better capture of MACE events. The selected database will be described in more detail in the US SAP.

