We anticipate that the US dataset will include >20,000 new users of Contrave who will be eligible for inclusion in the study as of December 31, 2022. The final analysis of the US database will be conducted and presented in a US only study report.

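### The censoring rule's single end date, 31 December 2023, matches neither the Nordic inclusion dates nor the US data receipt date, and the rule has no end-of-data or last-activity term

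*Protocol*

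**What the plan says.** **Censoring.** Section 9.3.2: "censoring will occur at the earliest of death, disenrollment, 548 days of follow-up, or end of the study period (December 31, 2023". The note under Figure 1 (section 9.3.1) has the same four terms: "Earliest of: death, disenrollment, 548 days of follow-up, end of the study period". Neither has a term for the end of available data or for last recorded activity, and neither varies by data source.

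**Who enters.** Criterion 1 (section 9.1.1) requires the prescription or dispensing to fall within the study period. Section 9.4.1.3 describes Norway's final analysis as "including all patients meeting the inclusion criteria for the study as of 31 December 2024", and section 9.7.1 describes the final analysis as "including all patients from the EU data sources meeting the inclusion criteria for the study as of 15 February 2025". For the US, section 9.4.2 expects more than 20,000 new users "eligible for inclusion in the study as of December 31, 2022".

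**US data.** Section 6 anticipates US data receipt on 15 February 2023 and the US final report on 4 August 2023. Section 9.4.2 says that "a sizeable proportion of the EHR population will also have their health insurance claims records linked", so only part of the population has claims. Appendix 3 (a draft list) marks US death, disenrollment and eligibility/enrolment dates as Partial. In the four Nordic sources, death and eligibility dates are marked Yes and disenrollment Partial.

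**Who stays, and which denominators.** Section 9.7.1 keeps all patients "regardless of whether there is evidence of any contact with the health system" after inclusion. Section 9.7.3 computes AESI rates on exposure time, which ends 4 weeks after the last prescription or dispensing. The synopsis and section 9.7.3.1 also call for rates over all person-time through 548 days.

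**The concern.** A censoring rule has to tell the programmer when each patient stops contributing time. Here it gives one calendar date for five sources whose data end at different times. The Nordic inclusion dates lie after that date and the US data receipt lies before it.

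In the Nordic sources the text leaves open whether anyone indexed in 2024 or later belongs in the cohort. In the US, the written rule allows person-time that the delivered data cannot contain. It also gives no stopping point for a patient who leaves the contributing health systems without a recorded exit. Such time carries no events because nobody is looking, so it pulls full-window rates down, towards apparent safety, in what is expected to be a very large source.

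**Working it through.** **Inputs.** End of study period 31 December 2023 (9.3.2). Window 548 days, which is 548/30.4375 = 18.0 months, as the protocol states. Inclusion dates 31 December 2024 (9.4.1.3), 15 February 2025 (9.7.1) and 31 December 2022 for the US (9.4.2). US data receipt 15 February 2023 and US report 4 August 2023 (section 6).

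**Nordic dates.** Follow-up allowed = 31 December 2023 − index date, capped at 548.
- Index 31 December 2024: −366 days.
- Index 15 February 2025: −412 days.

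A negative value means such a patient has no follow-up under the rule. Criterion 1 would also bar that patient, because the dispensing falls outside the study period. The passages are therefore consistent only if the later dates are data cuts, and they are not labelled so. If they are true accrual dates, the end of study period must move. Even then, an index on 31 December 2024 completes 548 days on 2 July 2026, and one on 15 February 2025 completes them on 17 August 2026. Both fall after the final report of 31 December 2025, so truncated follow-up would have to be accepted explicitly.

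**US dates.**
- Rule end minus data receipt: 31 December 2023 − 15 February 2023 = 319 days.
- Rule end minus report: 31 December 2023 − 4 August 2023 = 149 days.
- Index 31 December 2022: the rule allows 365 days and the data at most 46, so 365 − 46 = 319 days cannot be observed.
- Index 1 July 2022: the rule allows the full 548 days and the data at most 229 (1 July 2022 to 15 February 2023), so 548 − 229 = 319.
- 15 February 2023 − 548 days = 16 August 2021. For any later US index date the rule allows more time than the data can hold. The excess grows from 0 to 319 days by 1 July 2022 and stays at 319 after that.

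This step needs no assumption about loss to follow-up, only that data cannot extend past their planned receipt.

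**Unrecorded exits, US (assumed values).** Let *f* be the share of patients who leave without a recorded exit, and *m* the mean fraction of the window seen before they leave. With a constant event rate and no events seen after exit, recorded rate / true rate = 1 − *f*(1 − *m*).
- *m* = 0.5 (exits spread evenly): *f* = 10%, 20%, 40% gives 0.95, 0.90, 0.80.
- *f* from 5% to 40% and *m* from 0.25 to 0.75: the ratio runs from 0.99 down to 0.70.

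Neither *f* nor *m* is in the protocol.

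**Which rates are exposed.** Exposure time stops 4 weeks after the last prescription, so a patient who disappears stops accruing it soon after the last record. For a prescription written just before the cut, the overrun is at most 28 days. The all-person-time denominator has no such stop.

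**The case against.** A reader might infer that patients indexed in 2024 and 2025 will be analysed with no follow-up. The document does not establish that. Criterion 1 still applies to anyone meeting the inclusion criteria as of a later date, and the notes to section 6 expect the 2023 data from Norway and Finland in late 2024, which fits a data-cut reading. Against this, section 9.4.1.3 first counts Norwegian users eligible as of 31 December 2023 and then includes those eligible as of 31 December 2024, which reads like further accrual. Both readings remain open, so this is a contradiction to reconcile.

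A reader might also infer that every patient must have 548 days of data. The requirement of "at least 548 days of availability in the data after the index date of Mysimba" is mainly a test for admitting a database. Sections 9.2 and 9.3.2 define patient follow-up as up to 548 days. Shorter follow-up near the end date is ordinary staggered entry, and person-year denominators handle it.

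On the US side, keeping patients regardless of contact governs membership of the analysis set, and disenrollment censoring still applies where it is recorded. How to define disenrollment in EHR data may properly be left to the US SAP, and Appendix 3 lists an enrolment variable for continued engagement. An analyst would probably also stop at the data cut unprompted. These points reduce the likely harm. They do not cure a closed list that contains no such stop and names a date after the US report.

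Finally, the sentence setting the all-person-time denominator follows one on new comorbidities and concomitant medication, so its application to AESIs is not certain. It does stand in the section on AESI rates, and section 9.9.1 describes assessment over the whole 548 days.

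**Conclusion.** The point holds as an inconsistency in dates and a missing censoring term. For the Nordic sources, the end of study period and the inclusion dates disagree by 366 and 412 days and must be reconciled. For the US, the end date is wrong as written, by up to 319 days per patient, given the anticipated dates in section 6.

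A stronger claim, that the main US AESI rates are biased downward, is not supported: the exposure-time rate is largely protected. What is exposed is any US rate over all person-time to 548 days. The part due to unrecorded exits is unknown. If 20–40% left evenly over the window, about 10–20% of full-window person-time would be unobserved and those rates understated by that share; this is an assumption, not a finding. Nordic patients indexed early enough are little affected, since deaths and eligibility dates are marked as available there, although disenrollment is only Partial.

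**What to change.** 1. For each database, state one last index date and one end-of-data date, and use them consistently in sections 9.3.2, 9.4.1.1–9.4.1.4, 9.4.2 and 9.7.1. Label the 31 December 2024 and 15 February 2025 dates as data cuts, or move the end of study period to match them.
2. Add end of available data to the censoring list for all sources, in section 9.3.2 and under Figure 1. For US patients without enrolment dates, also add last recorded activity.
3. Report the US full-window rates on claims-linked enrolled time as a sensitivity analysis.
4. State that keeping patients regardless of later contact decides who is in the analysis set and does not extend US person-time.

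This is protocol wording plus one sensitivity analysis. The cost is somewhat less US person-time. Last-activity censoring may also slightly overstate rates, because patients who are well and stay away are censored early; the claims-linked analysis helps to show by how much. There is no need to close accrual at 1 July 2022 (the last index date with a full 548 days before 31 December 2023) or to confine the main US AESI analysis to claims-linked patients. Both would discard valid exposed time.
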